NCT#: NCT02240108

## SYNOPSIS

|                                 |   |
|---------------------------------|---|
| PROTOCOL TITLE:          | A Double-Blind, Placebo-Controlled, Parallel-Group, Multicenter, Multiregional, One Year Study to Assess the Efficacy and Safety of Twice Daily Oral Rifaximin Delayed Release Tablets for Induction of Clinical Remission with Endoscopic Response at 16 Weeks followed by Clinical and Endoscopic Remission at 52 Weeks in Subjects with Active Moderate Crohn's Disease  |
| PROTOCOL NUMBER:         | RECD3126  |
| SPONSOR:                 | Salix Pharmaceuticals, Inc.   |
| TREATMENT:               | Treatment A: Rifaximin Delayed Release (DR) Oral Tablets 800 mg BID administered continuously without dose-adjustment for 52 weeks

Treatment B: Matching placebo BID administered continuously without dose-adjustment for 52 weeks  |
| PRIMARY OBJECTIVE:       | To determine the efficacy of Rifaximin DR 800 mg BID vs. placebo for the induction of clinical remission and endoscopic response following 16 weeks of treatment in subjects presenting with active moderate Crohn's disease.   |
| KEY SECONDARY OBJECTIVE: | A key secondary objective is to evaluate clinical and endoscopic remission following an additional 36-week long term treatment phase of Rifaximin DR 800 mg BID vs. placebo.  |
| STUDY DESIGN:            | RECD3126 is a double-blind, placebo-controlled, parallel-group, multicenter, multiregional, 52-week study to assess the efficacy and safety of Rifaximin DR tablets for the induction of clinical remission and endoscopic response at 16 weeks followed by clinical and endoscopic remission after 52 weeks of continuous therapy in subjects with active moderate Crohn's disease. Subjects will be eligible if they have active, moderate disease defined by a Crohn's disease Activity Index (CDAI) score of $\geq 220$ and $\leq 450$ points at screening, and evidence of active ileocolonic Crohn's disease defined by a Simple Endoscopic Score for Crohn's disease (SES-CD) of $\geq 7$ on baseline ileocolonoscopy as assessed by blinded central reading. Eligible subjects will complete a 2- to 3-week Screening Period, a 52-week Treatment Period consisting of a 16-week Induction Phase and 36-Week Long Term Treatment Phase, and a 2-week Follow-up Period. Subjects will be randomized in a 1:1 allocation to Rifaximin DR 800 mg BID or placebo at the beginning of the treatment period and will maintain |

Confidential

|                                      |   |
|--------------------------------------|---|
|                                      | 
treatment assignment throughout the duration of the study. Ileocolonoscopy will be performed on all subjects at baseline (between Visits 1 and 2), between Weeks 16 and 17 (end of the Induction Phase), and following completion of the 36-week Long Term Treatment Phase (Week 52) to assess the effects of treatment on the degree of mucosal healing. Subjects will be assessed during clinic visits which are scheduled at Weeks 0 (baseline), 2, 4, 8, 12, and 16; then every four weeks through Week 52. All subjects will be required to complete a daily diary. All subjects will complete a 2-week (study drug free) Follow-up Period following completion of the 52-week Treatment Period, and will return to the clinic for final assessments (End-of-Study [EOS] visit; Week 54). See Figure 1.
   |
| STUDY DURATION:               | Per Subject: 2- to 3-week Screening Period, 52-week Treatment Period, and a 2-week Follow-up Period. The maximum duration of subject participation will be 57 weeks.  |
| SUBJECT POPULATION:           | Subjects with active, moderate disease defined by a CDAI score of $\geq 220$ and $\leq 450$ points at screening, and evidence of active ileocolonic Crohn's disease defined by a SES-CD score of $\geq 7$ as determined from baseline ileocolonoscopy.  |
| NUMBER OF SUBJECTS:           | Approximately 660 total: 330 to Treatment A (800 mg Rifaximin DR BID) and 330 to Treatment B (Placebo BID)  |
| NUMBER OF CENTERS:            | Approximately 200   |
| LOCATION:                     | United States, Canada, Russia, Israel and countries in Europe   |
| CO-PRIMARY EFFICACY ENDPOINT: | 
There will be two co-primary measures of efficacy assessed during the Induction of Clinical Remission and Endoscopic Response Phase. The first co-primary endpoint is:
 

• Clinical Symptom Remission defined by (1) the total number of liquid/very soft stools for the 7 days prior to the Week 16 visit being <math>\leq 10</math> (from CDAI Item 1); AND (2) an abdominal pain rating of <math>\leq 1</math> (from CDAI Item 2) on each day for the 7 days prior to the Week 16 visit.

 
The second co-primary endpoint is:
 

• Endoscopic Response defined as a <math>\geq 3</math>-point decrease in the SES-CD from baseline to the SES-CD score obtained between Week 16 and Week 17. SES-CD scores will be calculated from centrally-read digital video of ileocolonoscopies performed at

 |

Confidential

|                                   |  |
|-----------------------------------|--|
|                                   | baseline and between Week 16 and Week 17.  |
| KEY CO-SECONDARY ENDPOINT: | 
There will be two key co-secondary endpoints of efficacy assessed during the Long Term Treatment Phase. The first is:
 

• Clinical symptom remission defined by (1) the total number of liquid/very soft stools for the 7 days prior to the Week 52 visit being <math>\leq 10</math> (from CDAI Item 1); AND (2) an abdominal pain rating of <math>\leq 1</math> (from CDAI Item 2) on each day for the 7 days prior to the Week 52 visit.

 
The second is:
 

• Endoscopic remission defined as a SES-CD score of <math>\leq 2</math> at Week 52. SES-CD scores will be calculated from centrally-read digital video of ileocolonoscopies performed at Week 52

   |
| SECONDARY ENDPOINTS:       | 
The following secondary endpoints will be assessed:
 

• Induction of clinical remission defined as a CDAI score of less than 150 points at Week 16.

• Proportion of subjects with SES-CD score of 0 at Week 52.

• Clinical remission defined as a CDAI score of less than 150 points at post-baseline visits.

• Change from baseline in SES-CD score at Week 16 and Week 52.

• Clinical symptom remission over time: The total number of liquid/very soft stools for the 7 days prior to each clinic visit being <math>\leq 10</math> (from CDAI Item 1); AND (2) an abdominal pain rating of <math>\leq 1</math> (from CDAI Item 2) on each day for the last 7 days prior to each clinic visit in <math>\geq 80\%</math> of the study visits during the 52-Week Treatment Phase, including Week 52.

• Time to loss of CDAI response defined by a CDAI score of <math>\geq 150</math> points during the Long Term Treatment Phase.

• Time until durable response to the liquid/very soft stool component of the co-primary endpoint during the 52-Week Treatment Phase.

 |

Confidential

|                          |  |
|--------------------------|--|
|                          | 

• Time until durable response to the abdominal pain component of the co-primary endpoint during the 52-Week Treatment Phase.

• Proportion of subjects with response to the abdominal pain component of the co-primary endpoint at post-baseline time points.

• Proportion of subjects with response to the liquid/very soft stool component of the co-primary endpoint at post-baseline time points.

• Proportion of subjects who achieve clinical remission by the CDAI endpoint at post-baseline time points.

• Percentage of subjects who achieve clinical response at post-baseline time points. Clinical response is defined as a reduction of at least 100 points from the baseline CDAI score.

• Time to clinical response based on Week 16 co-primary endpoints.

 |
| SAFETY ENDPOINTS: | 

• Incidence, intensity, and types of adverse events (AEs).

• Changes from baseline in the laboratory parameters (hematology, clinical chemistry, urinalysis).

• Changes from baseline in vital sign measurements.

  |
| OTHER ENDPOINTS:  | 
Exploratory assessments will include:
 

• Characterization of stool microbiota at baseline and after 16 and 52 weeks of treatment.

▪ Baseline and post-treatment bacterial DNA isolated from stool for 16S rRNA gene amplification.

▪ Descriptive characterization of bacteria in stool by:

• Isolation and identification of selected Gram-negative and Gram-positive bacteria.

• Resistance to selected antibiotics, including rifaximin and rifampin.

• Genomic profiling of pregnane X receptor (PXR) in blood.

• Population pharmacokinetics of rifaximin.

   |

Confidential

|                     |   |
|---------------------|---|
| SAMPLE SIZE: | 
The information below provides the background information for sample size determination for the induction of clinical remission with endoscopic response at 16 weeks followed by clinical and endoscopic remission at 52 weeks. For placebo, the expected rates are based on data from a Phase 2 study (RETIC 03/06) conducted in subjects with active moderate Crohn's disease. The rates for Rifaximin DR are based on the assumption that Rifaximin DR will provide a somewhat higher induction of remission rate.
 
Expected rates for induction of clinical remission with endoscopic response at Week 16 are 40% for placebo and 55% for Rifaximin DR.
 
Based on a significance level of 5% (alpha 0.05), a sample size of approximately 240 subjects per treatment group will have at least 90% power to test the hypothesis that Rifaximin DR is superior to placebo for each co-primary endpoint considered individually. Approximately 80% power is available to detect significant differences between Rifaximin DR and placebo for each of the co-primary endpoints.
 
For the long term treatment phase, a 15% treatment effect is expected for both clinical symptom and endoscopic remission at Week 52. Based on this assumption and testing at a significance level of 5% (alpha 0.05), a sample size of approximately 210 subjects per treatment group will have at least 90% power to test the key secondary efficacy hypothesis that Rifaximin DR is superior to placebo when each key co-secondary endpoint is considered individually. In addition, approximately 80% power is available to detect significant differences between Rifaximin DR and placebo for each of the key co-secondary endpoints.
 
An additional consideration for sample size determination is the application of an inflation factor of 20% to account for drop-out rates during the Induction and Long Term Treatment Phases of the study. This consideration suggested that 330 subjects per treatment group would be required at study entry.
 |
|---------------------|---|

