3.2 Secondary Objective

A key secondary objective is to evaluate clinical and endoscopic remission following an additional 36-week Long Term Treatment Phase of Rifaximin DR 800 mg BID vs. placebo. The secondary objectives of this study are the following:

- Assess the safety of Rifaximin DR following a 16-week induction, and an additional 36-week Long Term Treatment Phase (i.e., up to 52 weeks of treatment for eligible subjects).
- Assess the population pharmacokinetics of Rifaximin DR.
- Characterize the gastrointestinal microbiota from stool samples, and antibiotic resistance from bacteria cultured from stool samples before and after treatment with Rifaximin DR.
- Evaluate the effects of Rifaximin DR treatment on indices of health outcomes.
- Assess the effects of Rifaximin DR treatment on biological (inflammatory) markers of disease.

This applies to both *RECD3125* and *RECD3126*.

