7 STATISTICAL ANALYSIS METHODS

7.1 General Considerations

All data for enrolled subjects will be presented in data listings by subject number.

Continuous data will be described using descriptive statistics: number of observations (n), mean, standard deviation (STD), median, minimum, and maximum. Frequencies and percentages will be used for summarizing discrete (categorical) data. When categorical data are presented, the percent will be suppressed when the count is zero. The denominator for all percentages, unless otherwise specified, will be the number of subjects in the specified analysis population.

For those summary tables in which baseline and change from baseline measurements will be presented, the baseline is defined subject to each specific analysis.

Safety data will be analyzed using the observed data. Missing values will not be imputed unless otherwise stated.

If additional analyses are required to supplement the planned analyses described in this SAP after database lock, they may be performed and will be identified in the CSR.

Statistical analyses and summaries will be performed using SAS® Version 9.3 or greater or other validated statistical software as required.

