7.3 Sample Size

For sample size justification, reference corresponding study protocols.

Originally planned sample sizes per arm for each of the studies are listed below:

Study	Treatment A: Rifaximin DR Tablets 800 mg BID	Treatment B: Placebo BID
RECD3125	330	330
RECD3126	330	330

Both studies will be terminated early therefore the actual sample size may vary.

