7.5 Analysis Population

The Intent to Treat (ITT) population will include all randomized subjects who take at least one dose of study drug.

The analyses of baseline characteristics, efficacy and safety will be performed for the ITT Population.

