7.8.3.1 Treatment-Emergent Adverse Events

A non-fatal AE is considered as a treatment emergent adverse event (TEAE), if the start date of the AE is within the period of first dose date of study medication and last dose date of study medication plus five days. A fatal AE is considered TEAE if the start date of the AE is within the period of first dose date of study medication and last dose of study medication plus 30 days.

The incidence of treatment-emergent AEs will be summarized by body system and MedDRA preferred term. If a subject reports the same AE more than once, then that subject will only be counted once for the summary of that AE, using the most severe intensity.

In case of incomplete or missing AE dates, the standard Salix estimation rule for AEs will be followed in order to determine whether an AE should be considered treatment-emergent. If the AE category still can't be determined, the AE will be considered as TEAE. The onset dates reported in the CRF will be presented in the listings.

Treatment-emergent AEs will be summarized as follows:

- All treatment-emergent AEs;
- All treatment-emergent AEs by intensity;
- All treatment-emergent AEs related to study drug;
- All treatment-emergent SAEs; and

- All treatment-emergent AEs that led to premature discontinuation of study drug.

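### Adverse events are planned only as crude percentages of all dosed subjects, which in a study that stops early estimate neither a 16-week nor a 52-week risk and understate the latter

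*Protocol*

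**What the plan says.** The endpoint line in the protocol synopsis, "Incidence, intensity, and types of adverse events (AEs", is unobjectionable. The choice of summary measure is made in the SAP.

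- **Measure (SAP 7.8.3.1; Protocol 8.6.5 agrees):** "The incidence of treatment-emergent AEs will be summarized by body system and MedDRA preferred term". A subject who reports the same event more than once is counted once: "that subject will only be counted once for the summary of that AE, using the most severe intensity".
- **Denominator (SAP 7.1):** "The denominator for all percentages, unless otherwise specified, will be the number of subjects in the specified analysis population". SAP 7.5 supplies the population: "The analyses of baseline characteristics, efficacy and safety will be performed for the ITT Population", and "The Intent to Treat (ITT) population will include all randomized subjects who take at least one dose of study drug". Nothing in SAP 7.8.3 specifies otherwise.
- **Window (SAP 7.8.3.1):** a non-fatal event counts if it starts between first dose and last dose plus five days; for a fatal event the limit is last dose plus 30 days. SAP 7.8.3, one paragraph earlier, defines treatment-emergent from Visit 2 with no end date.
- **Exposure (SAP 7.8.1):** duration is summarised by arm in its own table and is not linked to the event tables.
- **Phase:** disposition (SAP 7.6.1) and vital signs (SAP 7.8.6) are split by study phase. Adverse events are not.
- **Objective (SAP 3.2):** "Assess the safety of Rifaximin DR following a 16-week induction, and an additional 36-week Long Term Treatment Phase".
- **Early stop (SAP 7.3):** "Both studies will be terminated early therefore the actual sample size may vary". SAP section 8 lists the analyses dropped for that reason but does not adapt the adverse event analysis.

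**The concern.** The objective names two time horizons; the planned summary has none. A subject on drug for 4 weeks carries the same weight in the denominator as one on drug for 52, and because the non-fatal window follows dosing, a subject who leaves early has little chance to contribute an event. When planned treatment is 52 weeks and many subjects will not reach it, the percentage is an average over whatever exposure accrued. A reader of the study report, or of a pooled summary of the two studies, is likely to take it as the risk over a one-year course, and it is lower than that. The report would also not show whether events cluster in induction or continue through long-term treatment.

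**Working it through.** **Inputs from the documents.** Treatment lasts 52 weeks (16 + 36). Entry is 330 per arm; 240 per arm are required at Week 16 and 210 at Week 52; a 20% drop-out factor applies (Protocol 8.2). Randomisation is 1:1 within centre (Protocol 8.1, SAP 7.2). Both studies stop early (SAP 7.3, section 8).

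**Not in the documents, so assumed.** Event risks, drop-out by arm, stop date and number enrolled. Event hazards are taken as constant, and drop-out as independent of events and exponential within phase. The five-day tail is ignored.

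**1. The plan's own figure.** A single 20% allowance does not give 330: 240/0.8 = 300 and 210/0.8 = 262.5. Applied once per phase it nearly does: 210/(0.8 × 0.8) = 328.1, so 329 against 330. The protocol does not state this reading, but it implies 0.8 × 0.8 = 64% still on treatment at Week 52. I use it as one scenario.

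**2. Crude percentage with 20% loss per phase, true 52-week risk 20%.** Weekly rates:
- event: λ = −ln(0.80)/52 = 0.004291
- loss in induction: δ1 = −ln(0.80)/16 = 0.013946
- loss in long-term treatment: δ2 = −ln(0.80)/36 = 0.006198

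First events over all dosed subjects:
- Weeks 0–16: λ/(λ+δ1) × [1 − exp(−16(λ+δ1))] = 0.05955
- still on drug and event-free at Week 16: exp(−16 × 0.018238) = 0.7469
- Weeks 16–52: 0.7469 × λ/(λ+δ2) × [1 − exp(−36(λ+δ2))] = 0.09610
- total: 0.05955 + 0.09610 = 0.1557, i.e. **15.6% against 20%**

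Mean exposure is 0.2/δ1 + 0.8 × 0.2/δ2 = 14.34 + 25.81 = 40.15 weeks. By the same formula:

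| True 52-week risk | Crude percentage |
|---|---|
| 5% | 3.9% |
| 10% | 7.8% |
| 20% | 15.6% |
| 40% | 31.4% |
| 60% | 47.8% |

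If 20% is instead the total loss over 52 weeks, a true 20% shows as 18.0%.

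**3. Early termination.** If follow-up is spread evenly over 0–52 weeks (mean 26) and the event rate is 0.3 per year, the crude percentage is 1 − (1 − e^−0.3)/0.3 = **13.6%**, against a one-year risk of 1 − e^−0.3 = **25.9%**. Combining 20% loss per phase with uniform enrolment over 52, 104 or 156 weeks followed by a stop, a true 20% shows as 8.6%, 12.1% or 13.2% (mean exposure 21.5, 30.8 or 33.9 weeks).

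**4. Between arms.** A study-wide stop under 1:1 allocation within centre shortens follow-up about equally in both arms. It lowers both percentages and shrinks the absolute difference, but should not create one. Unequal drop-out could. As pure hypotheticals with no drug effect on events and event rates of 0.1 to 0.7 per year, loss by Week 52 of 45% on placebo and 27% on drug gives a crude risk ratio of 1.12 to 1.14; 50% and 22% gives 1.20 to 1.22. Adding a stop time uniform over 0–52 weeks reduces these to 1.08–1.09 and 1.13–1.14. None of these splits has a source in the documents.

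**5. Which remedy.** Keep the same two hypothetical splits and no drug effect, but let events occur only in the first 8 weeks. The crude ratio is 1.02 (45%/27%) or 1.03 (50%/22%). The ratio of overall rates per person-year is 0.90 or 0.84, because later event-free time dilutes the rate more in the arm that stays longer. Cumulative incidence at a fixed time gives 1.00 under independent drop-out. A single overall person-time rate is therefore not a safe replacement.

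**The case against.** Neither document calls the percentage a 52-week risk. It is a valid description of events during actual exposure, and the tables are descriptive with no planned test. Exposure by arm and disposition by arm, phase and reason are already tabulated, so an imbalance would be visible. The report is to be abbreviated. All of this stands, and it keeps the point from being serious. It does not close the gap: mean exposure by arm yields neither time to first event nor a phase-specific risk, and the objective names both horizons.

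Two stronger readings are tempting.

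- **That unequal exposure will create or hide a difference between arms.** Worsening disease is a listed reason for discontinuation (Protocol 4.5), so drop-out could differ by arm. The documents give no drop-out by arm, however, and early termination acts on both arms alike. Any risk ratio is hypothetical.
- **That rescue treatment masks drug events.** Protocol 4.3.2 keeps rescued subjects in the study. The documents do not say whether they continue study drug, and the non-fatal window closes five days after last dose, so the masking is conjecture. Ending time at risk at rescue could also introduce informative censoring.

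It is also fair to say that person-time rates carry assumptions of their own. Step 5 above confirms it and shapes the fix.

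**Conclusion.** The point holds as one about estimation. The planned percentage is neither a 16-week nor a 52-week risk, and read as the latter it is too low: 15.6% for a true 20% at an assumed 20% loss per phase, and 13.6% for a true 25.9% with follow-up uniform over 0–52 weeks. The direction follows from the SAP's counting rule and window. The size rests on constant hazards, independent drop-out and an assumed exposure pattern, because the documents give no stop date, enrolment count or exposure. They do not support a claim that the arm comparison is biased. This is a cheap improvement, between optional and recommended, and not an error that invalidates the safety tables.

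**What to change.** 1. Reconcile the two definitions of treatment-emergent in SAP 7.8.3 (no end date) and 7.8.3.1 (last dose plus 5 days, or plus 30 if fatal). Time at risk cannot be programmed until one is chosen.
2. In SAP 7.8.3.1 keep n (%). For all TEAEs, related TEAEs, TEAEs leading to discontinuation and serious TEAEs, add:
   - the cumulative incidence of first event by arm at Week 16 and Week 52 (Kaplan-Meier, or Aalen-Johansen where a competing event matters), with time at risk ending at the close of the reconciled window, numbers at risk shown, and the difference with 95% CI;
   - person-years at risk and first events per 100 person-years by phase (Day 1 to Week 16; after Week 16), labelled descriptive.
3. State the assumptions: both estimates take drop-out as non-informative, and the rates also take the hazard as roughly constant within phase. Few subjects may be at risk near Week 52 after an early stop, so that estimate may be imprecise.

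The cost is SAP wording, programming and a few more safety tables. Dose dates and adverse event dates are already collected; no protocol change or new data are needed.
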